Statistics	
Primary and secondary objectives will be analyzed using the Complete Case Analysis Set that will include all subjects who initiate the aDBS treatment phase and have complete data for the respective analysis. Safety analyses will be evaluated using the As-Treated (AT) Analysis Set. AT includes all subjects who are treated with continuous Deep Brain Stimulation (cDBS) and/or adaptive Deep Brain Stimulation (aDBS) at enrollment and/or the aDBS treatment phase and uses the observed treatment used for each subject in each phase. The change in TEED will be used to evaluate the primary objective. A paired t-test will be used to compare the difference in TEED for aDBS (Single or Dual mode) to cDBS. Normality of the outcome will be assessed with the Shapiro-Wilk test. If large violations to the normality assumption are observed ($p < 0.05$), the primary analysis will use a Wilcoxon signed-rank test to assess statistical significance.
 
The secondary endpoint of mean percent time in Beta window inside the predefined window will be assessed based on data collected from the Percept device using Brain Sense Timeline View function and will be analyzed using a paired t-test or nonparametric Wilcoxon Rank-Sum of % of time in the window for the preferred aDBS mode vs cDBS.
 
The Gatekeeping procedures will be applied for the multiple testing procedures. After the primary study objective is met ($\alpha = 0.05$ two-sided, gatekeeper), the secondary study objective will be carried out at $\alpha = 0.05$ two-sided. No multiplicity adjustment will be performed for evaluations of the additional study objectives. No imputation will be used.

3. Introduction

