11.8 Product Complaint Reporting

Product complaint reporting and vigilance reporting are applicable and DDs and AEs related to any market released device during the study must be reported. The reporting of product complaints except for all reportable AE information for this study is not part of the study and should be done in addition to the AE reporting requirements. Refer to local regulations for reporting requirements.

Product Complaint: Any written, electronic or oral communication that alleges deficiencies related to the identity, quality, durability, reliability, safety, effectiveness or performance of a medical device that has been placed on the market.

It is the responsibility of the PI/ Sub investigator to report all product complaint(s) associated with a

medical device distributed by Medtronic, regardless whether they are related to intended use, misuse or abuse of the product. Reporting must be done immediately and via the regular channels for market-released products. Medtronic will notify the Ras (e.g. CA) as applicable in accordance with the requirements upon learning of them and is not limited to AEs and DDs only.

12. Statistical Design and Methods

The study participants will be randomized to either sequence: the first treatment is aDBS and then cDBS, or the first treatment is cDBS then aDBS. According to the randomized sequence, the first treatment DBS mode is started in Period A and second DBS mode is started in Period B. Supporting analyses for the primary objective include verifying the lack of a period or carryover effect in randomized subjects.

The Early Adapter Part II study will be considered successful when the primary objective of the study is met. The main analysis of primary and secondary objectives will use the Complete Case set (CC) which include all subjects who initiate the aDBS treatment phase and have complete data for the respective analysis. The main analysis will include data from all sites. An assessment for poolability of the results across clinical sites will be conducted by descriptive analyses for individual sites for the primary and key secondary endpoint. Subject disposition will be reported in a CONSORT diagram to show the flow of participants through stages of the study.

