Directional Stim Mode may be programmed during the follow-up phase. The primary endpoint on the difference in TEED will be assessed by means paired t-test to compare the difference in TEED for aDBS (preferred mode, single or dual threshold) to cDBS. Normality of the outcome will be assessed with the Shapiro-Wilk test. If large violations to the normality assumption are observed ($p < 0.05$), the primary analysis will use a Wilcoxon signed-rank test to assess statistical significance.

To compute TEED using the formula above, the average current drain from the JSON session data will be computed using the average stimulation currents from the timeline feature in the 14 days prior to the visit. This will be computed as the average of the currents from the timeline feature using the epochs that align with the analysis set (e.g., As-Treated analysis set uses the actual aDBS mode as reported from the device). The pulse-width, frequency, and impedance will be determined from the JSON session data as per study procedure.

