12.5 Secondary Objective

The following secondary objective has specific hypothesis to be tested. This key secondary objective will be tested under a Gatekeeping strategy for the multiple testing procedures. After the primary study objective is met (gatekeeper), this secondary study objective will be carried out at $\alpha=0.05$ and a p-value less than 0.05 two-sided will be considered met as long as the primary objectives above it have also been met.

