12.5.1. Secondary Objective #1

The secondary objective is to demonstrate maintenance within an optimal beta LFP threshold of beta LFP power during aDBS mode compared to cDBS.

The formal hypothesis testing is:

$$H_0: \mu_{\text{LFPaDBS}} = \mu_{\text{LFPcDBS}}$$

$$H_a: \mu_{\text{LFPaDBS}} \neq \mu_{\text{LFPcDBS}}$$

The secondary endpoint is the mean percent time within an optimal beta LFP threshold of beta LFP power during aDBS mode compared to cDBS. The optimal beta LFP threshold indicates values between upper and lower LFP threshold preset for each patient.

The secondary endpoint will be assessed based on data collected from the Percept device using Brain Sense Timeline View function and will be analyzed using a Paired T-test or nonparametric Wilcoxon Rank-Sum Test according the LFP normal or non normal distribution between percent of time in the window for the preferred aDBS mode vs cDBS.

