7.9.2.3 Analysis methods

The secondary endpoint will be assessed based on data collected from the Percept device using Brain Sense Timeline View function. Denote the LPF on aDBS by LFP_{aDBS} and the corresponding value for cDBS by LFP_{cDBS} . For each patient the difference between LFP_{aDBS} and LFP_{cDBS} will be calculated ($LFP_{aDBS} - LFP_{cDBS} = LFP_{DIFF}$). The mean percent time within an optimal threshold calculation will be provided by Rune Labs according to the Appendix A. The endpoint will be analyzed using a Paired T-test or nonparametric Wilcoxon Rank-Sum Test according the LFP normal or non-normal distribution between percent of time in the window for the preferred aDBS mode vs cDBS.

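### The non-parametric fallback for the gatekept secondary endpoint is an independent-samples test applied to paired data; if it is used, its p-values are wrong and power can fall

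*SAP*

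**What the plan says.** The secondary endpoint is the mean percent of time that beta LFP power stays between each patient's preset lower and upper thresholds, compared between aDBS and cDBS.

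- **SAP 7.9.2.3** first sets up a paired quantity: "For each patient the difference between LFP_{aDBS} and LFP_{cDBS} will be calculated". It then gives the test: "The endpoint will be analyzed using a Paired T-test or nonparametric Wilcoxon Rank-Sum Test according the LFP normal or non-normal distribution". The comparison is "between percent of time in the window for the preferred aDBS mode vs cDBS".
- **Protocol 12.5.1** has the same rule: "will be analyzed using a Paired T-test or nonparametric Wilcoxon Rank-Sum Test according the LFP normal or non normal distribution".
- **Protocol section 2 (synopsis, Statistics)** again: "will be analyzed using a paired t-test or nonparametric Wilcoxon Rank-Sum of % of time in the window".
- **Protocol section 12 (opening paragraph)** gives the two randomised sequences: "the first treatment is aDBS and then cDBS, or the first treatment is cDBS then aDBS". Every patient who completes both periods therefore contributes a value under each mode.
- **Protocol 12.5** makes this the only secondary hypothesis behind the gatekeeper; "a p-value less than 0.05 two-sided will be considered met" once the primary objective has been met.

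For the primary endpoint, TEED, which has the same paired structure, protocol 12.4 says that under non-normality "the primary analysis will use a Wilcoxon signed-rank test to assess statistical significance". SAP 7.9.1.4 agrees.

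**The concern.** The paired t-test and its fallback should answer the same question about the same within-patient differences. The signed-rank test does that. The rank-sum test pools the aDBS and cDBS values, ranks them as if they came from different people, and uses a null distribution that holds only if the two sets are independent. Here both values come from the same patient, leads and preset thresholds, so some positive correlation is expected.

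The same term stands in all three places, so checking one document against the other would not reveal it, and nothing elsewhere corrects it. At stake is the one secondary claim that the protocol tests formally. If the fallback is used, a real improvement in time within the window could be missed. Changing the test after the data have been seen would look post hoc.

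**Working it through.** **1. The plan's own figure.** The only power statement concerns TEED: 20 subjects, two-sided 0.05, at least 90% power (protocol 12.8; SAP 6). For a paired t-test the non-centrality is (difference / SD) × √n, with 19 degrees of freedom and critical value 2.093.

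- SAP: 28/36 = 0.778; 0.778 × √20 = 3.48; power 0.910.
- Protocol: 22/28 = 0.786; 0.786 × √20 = 3.51; power 0.915.

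Both reproduce. Neither applies to the secondary endpoint, for which no effect, SD, correlation or power is given. Everything below on size therefore rests on assumed inputs.

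**2. Why the p-value is wrong.** Let each mode have variance σ² and let ρ be the within-patient correlation. The variance of the mean difference is 2σ²(1 − ρ)/n; an independent-samples test uses 2σ²/n. Its statistic is therefore too small by a factor √(1 − ρ). In large samples, rejecting at 1.96 amounts to requiring 1.96/√(1 − ρ) on the correct scale:

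- ρ = 0: 1.96, so the actual level is 0.05.
- ρ = 0.5: 1.96/0.707 = 2.77, so the level is about 0.006.
- ρ = 0.7: 1.96/0.548 = 3.58, so the level is about 0.0003.

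This is a mean-based approximation. The rank-sum test at n = 20 is a little less extreme (step 3), in the same direction.

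**3. Simulation, n = 20 pairs, normal data, two-sided 0.05.** Type I error and power at a standardised paired effect of 22/28, borrowed from the primary endpoint:

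| Assumed ρ | Rank-sum type I error | Rank-sum power | Signed-rank power |
|---|---|---|---|
| 0 | 0.049 | 0.91 | about 0.90 |
| 0.3 | 0.020 | 0.83 | about 0.90 |
| 0.5 | 0.009 | 0.71 | about 0.90 |
| 0.7 | 0.002 | 0.43 | about 0.90 |
| 0.8 | 0.0003 | 0.21 | about 0.90 |

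The signed-rank type I error stays at 0.046 to 0.050 throughout. At ρ = −0.3 the rank-sum type I error is 0.084.

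At a smaller assumed effect of 0.66 SD of the difference, rank-sum power is about 52% against 79% at ρ = 0.5, and about 25% against 78% at ρ = 0.7. Hand check: 0.66 × √20 = 2.95. With the thresholds from step 2, power is roughly Φ(2.95 − 2.77) = Φ(0.18) = 0.57 at ρ = 0.5 and Φ(2.95 − 3.58) = Φ(−0.63) = 0.26 at ρ = 0.7, close to the simulated values.

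**4. Other distributions, same n.**

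- Bounded percentages with heavy-tailed errors, centred near 50%, effect tuned to about 90% signed-rank power: rank-sum power is 0.80, 0.63, 0.29 and 0.10 at correlations of about 0.38, 0.56, 0.74 and 0.83, against 0.89 to 0.91.
- Strongly skewed (lognormal) data: rank-sum type I error is still wrong (0.009 at ρ = 0.5), but power is 0.981 against 0.978 at 0.5, 0.939 against 0.979 at 0.7, and 0.868 against 0.977 at 0.8. The loss is nil, 4 points and 11 points.

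**5. The whole two-step rule.** The loss counts only when the fallback is triggered. Taking Shapiro-Wilk at 0.05 on the differences as the trigger, at correlations of 0.5 to 0.7, the loss in overall power is 1 to 2 points for percentages centred near 50%. It is 13 to 47 points for percentages piled up near 100%.

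**The case against.** The best defence is that a rank-sum test can be valid in a two-period crossover when it compares within-patient period differences between the two sequence groups. The text does not describe that. It compares modes, and it defines the difference as aDBS minus cDBS.

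The other objections limit the size of the point, and they largely stand.

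- **The harm is conditional.** The fallback applies only under non-normality, whereas the headline simulation uses normal data and applies the rank-sum test to every trial. A percentage lies between 0 and 100, but that does not make within-patient differences non-normal. With logit-normal percentages centred near 50% and latent correlations of 0.5 and 0.7, Shapiro-Wilk on the differences triggered the fallback in about 4–6% of simulated trials. Overall power was then 0.80 and 0.74, against 0.82 and 0.76 with a signed-rank fallback. A reader might infer that most of the power is lost in any event; the documents give no basis for that.
- **The direction is conservative.** A reader might infer that wrong p-values mean a raised false-positive rate. That would need negative within-patient correlation, which nothing in the documents suggests.
- **The trigger is ambiguous rather than plainly wrong.** A reader might infer that normality is to be checked on raw LFP values. SAP 7.9.2.3 uses LFP as its label for the endpoint and defines the per-patient difference just before the test, so the phrase can also refer to the between-mode difference. What is clear is that no normality test or cut-off is stated for this endpoint, unlike the primary.
- **The stakes are limited.** Protocol section 12 rests study success on the primary objective alone, and its fallback is the right one.

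**Conclusion.** The named fallback is wrong as written: an independent-samples test is prescribed for paired data in three places. Its p-values are invalid whenever the two values on a patient are correlated.

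How much this matters cannot be settled from the documents. It depends on the within-patient correlation, the effect, the shape of the data and how often the fallback is triggered, and the plan states none of these. Across the assumptions examined, overall power loss runs from none (correlation 0), through 1 to 2 points (fallback rarely triggered), to 13–47 points (percentages crowded near the upper bound, correlation 0.5 to 0.7).

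It should be corrected before analysis, but it ranks below the defects that must be fixed for the trial to be interpretable. It touches a contingent step for a secondary endpoint and leaves the primary analysis, the sample size and the safety assessment unchanged.

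**What to change.** Make the same change in the protocol synopsis, protocol 12.5.1 and SAP 7.9.2.3:

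1. Replace the rank-sum test with the Wilcoxon signed-rank test on the within-patient difference in percent time (LFP_DIFF, aDBS minus cDBS).
2. State the trigger: Shapiro-Wilk applied to LFP_DIFF, with the signed-rank test used if p < 0.05, as for the primary endpoint.

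If a sequence-group analysis was in fact intended, say so instead and define it as a rank-sum comparison of period differences between the two randomised sequences.

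The cost is wording only: no new data and no change in sample size. At n = 20 and a standardised effect of 22/28 (assumed for this endpoint), the signed-rank test has power of about 0.90 for normal data whatever the correlation.

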7.9.2.4 Handling of missing data

All attempts will be made to minimize missing data. If missing data are observed, no imputation will be used for this analysis.

7.9.3 Additional Objectives

The additional objectives will be summarized by reporting:

- mean score in cDBS,
- mean score in aDBS,
- the estimated difference from aDBS to cDBS and the 95% confidence interval (CI) and reported separately by aDBS (preferred mode, single or dual threshold).

The Complete Case analysis set will be used for the additional objectives. No multiplicity adjustment will be performed for evaluations of the additional study objectives and no imputation of missing data will be used.

To characterize clinical outcomes of aDBS (preferred mode) vs. cDBS, and by aDBS mode in the following items:

- EQ-5D-5L
- Parkinson's Disease Questionnaire (PDQ)-39
- Unified Dyskinesia Rating Scale (UDysRS)
- Movement Disorder Society-Sponsored Revision of Unified Parkinson's Disease Rating Scale (MDS-UPDRS) II ("best" and "worst" conditions)*
- MDS-UPDRS III and IV
- LFP dynamics based on out of clinic patient event markers and PD Medication cycle
- Movement and sleep data collected from Apple Watch (will be correlated with Percept Device data and clinical measures)
- To assess a patient-specific anatomy using a visualization tool of lead location and simulated volume of neural activation based on Pre-op/post-op imaging data of Percept PC implant.
- Patient preference of aDBS (preferred mode) vs cDBS
- Patient satisfaction with aDBS (preferred mode)
- Global Impression of Change (GIC) with aDBS
- Assess the average function of the subjects during the past week, including the assessment date, when they were in the "best conditions" and "worst conditions".

* "Best conditions" is the time period when PD subjects are receiving relief from their Parkinson's disease symptoms. "Worst conditions" is the time period when PD subjects are not receiving relief from their Parkinson's disease symptoms.

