12.1 General Aspects of Analysis

Data analysis will be performed by Medtronic-employed statisticians or designees. All statistical analyses will be performed using Statistical Analysis System (SAS) for Windows (version 9.4 or higher, SAS Institute Inc. Cary, NC), R (version 3.2 or higher, R Foundation for Statistical Computing, Vienna, Austria) or any validated statistical software.

In the primary analysis report, continuous data will be summarized using standard descriptive statistics including the mean, standard deviation, median and range or interquartile range. Categorical variables will be summarized using frequency counts and percentages. For events that can occur more than once in a single subject, such as adverse events, the percentage will be based on subjects experiencing the event; both subject and event counts will be reported. P-values will be two-sided, with values less than 0.05 indicating statistical significance.

Since the impact of missing data is expected to be small no multiple imputation method for missing data is planned.

The Gatekeeping procedures will be applied for the multiple testing procedures. After the primary study objective is met ($\alpha=0.05$, two-sided gatekeeper), the secondary study objective will be carried out at $\alpha=0.05$ two-sided. No multiplicity adjustment will be performed for evaluations of the additional study objectives. No imputation will be used.

The analyses will use two population sets:

- The Complete Case set (CC) analysis includes all patients enrolled in the study those sign Patient Informed Consent, fulfill the inclusion and exclusion criteria and randomized who initiate the aDBS treatment phase and have complete data for the respective analysis. The CC set will be used for primary and secondary objectives.
- The As-Treated Set (AT) includes subjects who are treated with continuous Deep Brain Stimulation (cDBS) and/or adaptive Deep Brain Stimulation (aDBS) at enrollment and/or the aDBS treatment phase and uses the observed treatment used for each subject in each phase. This set will be used for safety assessment.

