12.7 Additional Objective(s)

The additional objectives will be summarized by descriptive statistics and reported separately for aDBS and cDBS and by aDBS (preferred mode, single or dual threshold). No multiplicity adjustment will be performed for evaluations of the additional study objectives and no imputation of missing data will be used. The Complete Case analysis set will be used for the additional objectives.

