12.8 Target Sample Size and Justification

Target sample size: 20-30 subjects

[Rationale for the sample size]

Based on the registry data and the bench testing, a conservative estimate based on the first quartile of TEED data for initial devices in the registry, TEED is expected to decrease between 35 and 22 units for aDBS single threshold mode and aDBS dual threshold mode, respectively^{56,57}. Due to the expected 5% of single threshold with bilateral aDBS with an expected TEED difference of 35 units, 25% of subjects in single threshold but with unilateral aDBS with an expected TEED difference of 18 units and 70% in dual threshold with an expected TEED difference of 22 units, we assume a difference of 22 units defined as the weighted average of those differences. A SD of 28 results in a medium to large effect size of 0.79⁵⁸. Based on these assumptions, the sample size was estimated using a two-sided (alpha=0.05) paired T-Test means (PASS 2019) to compare the difference in aDBS TEED to cDBS TEED of 22 and a standard deviation of 28, a minimum of 20 subjects achieves at least 90% power for the detection of an effect size of 0.79.

it is estimated that between 20-30 subjects implanted with a commercially available Medtronic DBS system with Percept PC INS will be enrolled to obtain a study population of 20 subjects who complete the aDBS treatment phase. .

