7.1.3 Analysis Sets

The following subject sets will be used for the analysis:

- Complete Case (CC): includes all subjects with bilateral aDBS who initiate the aDBS treatment phase and have complete data for the respective analysis. This set will be used for the primary analysis.
- As-Treated (AT): includes all subjects who are treated with continuous Deep Brain Stimulation (cDBS) and/or adaptive Deep Brain Stimulation (aDBS) at enrollment and/or the aDBS treatment phase and uses the observed treatment used for each subject in each phase regardless unilateral or bilateral DBS. This set will be used for the safety assessment.
- Lead Complete Case (LCC): includes all subjects with aDBS who initiate the aDBS treatment phase and have complete data for the respective analysis regardless of unilateral or bilateral aDBS. This set will be used for the supporting analysis.

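### The SAP carries a bilateral-only restriction into the additional objectives without a reason, dropping about a quarter of subjects and, under the protocol's planning mix, probably leaving too few single-threshold subjects for a confidence interval

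*SAP*

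**What the plan says.** SAP 7.9.3 asks for the mean score under cDBS, the mean score under aDBS, and "the estimated difference from aDBS to cDBS and the 95% confidence interval (CI) and reported separately by aDBS (preferred mode, single or dual threshold"). It fixes the population in one sentence: "The Complete Case analysis set will be used for the additional objectives".

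SAP 7.1.3 defines the CC set so that it "includes all subjects with bilateral aDBS who initiate the aDBS treatment phase and have complete data for the respective analysis". A second set, Lead Complete Case (LCC), covers those who "have complete data for the respective analysis regardless of unilateral or bilateral aDBS. This set will be used for the supporting analysis".

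The protocol also assigns the CC set to the additional objectives (12.7), with results "reported separately for aDBS and cDBS and by aDBS (preferred mode, single or dual threshold"). Its CC set (12.1) covers eligible subjects who were "randomized who initiate the aDBS treatment phase and have complete data for the respective analysis", with no condition on laterality. Protocol 12.7 promises descriptive statistics; the confidence intervals are added by the SAP.

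On the expected composition, protocol 12.8 gives: "Due to the expected 5% of single threshold with bilateral aDBS with an expected TEED difference of 35 units", then "25% of subjects in single threshold but with unilateral aDBS with an expected TEED difference of 18 units and 70% in dual threshold". SAP section 6 expects around 25% of subjects to be unilateral and excludes them from the primary analysis, but gives no split by mode.

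**The concern.** Describing outcomes by aDBS mode is a stated objective (protocol 4.1.4, SAP 4.4). In the protocol's mix the unilateral subjects are all single-threshold, so a bilateral-only set removes most of that mode from the tables meant to describe it. It also removes about a quarter of subjects from the overall aDBS-versus-cDBS estimates, although they are assessed in both periods like everyone else.

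The restriction appears in the SAP's TEED sizing and in the definition of the set for the primary analysis. Whatever its merit there, the SAP does not say why it should apply to quality of life, dyskinesia or motor scores. Protocol 12.2 requires departures from its planned methods to be documented in the SAP with a statistical rationale, and none is given here.

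**Working it through.** **Inputs**
- Mix (protocol 12.8): 5% single-threshold bilateral, 25% single-threshold unilateral, 70% dual-threshold.
- Target (SAP section 6): 20 bilateral subjects, 20 to 30 enrolled, around 25% unilateral.
- Assumptions: all dual-threshold subjects are bilateral (inclusion criterion 3 requires this only of those who tolerate dual mode alone); unilateral in SAP section 6 means unilateral aDBS, since all subjects have bilateral leads; no attrition.

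**The plan's own figures reproduce**
- Protocol weighted difference: 0.05 × 35 + 0.25 × 18 + 0.70 × 22 = 21.65, rounded to 22.
- Paired t-test, two-sided 0.05, n = 20: power is 91.5% for 22/28 (protocol) and 91.0% for 28/36 (SAP). In both cases 20 is the smallest n reaching 90%.

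**Single-threshold subjects in the SAP's CC set**
- Share lost: 25/(5 + 25) = 25/30, or five of every six.
- Share of the bilateral set: 5/(5 + 70) = 1/15 = 6.7%.
- Expected among 20: 20 × 1/15 = 1.33.
- Binomial(20, 1/15): P(0) = 25.2%, P(1) = 35.9%, so P(at most 1) = 61.1%, P(2 or more) = 38.9% and P(5 or more) = 0.9%.
- If 20 to 30 are enrolled and 75% are bilateral, 1.0 to 1.5 are expected.

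**Precision**

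The 95% CI half-width, in SDs of the within-subject difference, is t(0.975, n−1)/√n.

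| n | half-width (SD) |
|---|---|
| 1 | not estimable |
| 2 | 8.98 |
| 3 | 2.48 |
| 6 | 1.05 |
| 8 | 0.84 |
| 9 | 0.77 |
| 20 | 0.47 |
| 27 | 0.40 |

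**The same rows on LCC**
- Single-threshold subjects: 30% of 20 to 30 is 6 to 9, half-width 1.05 to 0.77 SD.
- When 20 are bilateral, LCC holds 20/0.75 = 26.7, about 27 subjects, of whom 0.30 × 26.7 = 8 are single-threshold (0.84 SD).
- Overall: 0.47 SD at n = 20 becomes 0.40 SD at n = 27.
- Unilateral share of the single-threshold row: 25/30 = 83%.

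**Sensitivity to the mix**

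The protocol mix restricted to bilateral subjects averages (0.05 × 35 + 0.70 × 22)/0.75 = 22.9, not the 28 on which the SAP is sized. If 28 is read as a blend of 35 (single) and 22 (dual), the single share is (28 − 22)/(35 − 22) = 46%, about 9 of 20. The SAP does not state that blend; it is an inference.

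**The case against.** A reader might infer that the single-threshold results cannot be produced at all. The documents do not support that. The 5% is a planning expectation. Even if it holds, there is a 39% chance of two or more such subjects, and with one subject the two scores and their difference can still be reported. Only the SD and the interval fail.

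Nor does the problem reach every additional objective. Satisfaction (SAP 7.9.3.8) is summarised for aDBS without a split by mode. Preference and global impression of change (7.9.3.5, 7.9.3.9) are categorical summaries. LFP dynamics (7.9.3.6) specifies no interval, and the correlations with watch data (7.9.3.7) are visual. The interval problem concerns the continuous scores: EQ-5D index and VAS, PDQ-39, UDysRS and MDS-UPDRS.

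Four further points count on the other side:
- The count of about 1 rests on a mix found only in the protocol. The SAP's sizing could imply as many as 9. This stands, and the size needs that range.
- SAP 7.2 provides intervals as appropriate, and SAP 7.11 lets lesser changes be justified in the study report. An analyst could therefore leave out an empty interval. That tidies the table but does not bring back the excluded subjects.
- The objectives are descriptive and carry no test. This stands, and it limits the seriousness of the point.
- A bilateral-only table compares like with like, whereas the LCC single-threshold row would be mostly unilateral and the dual row bilateral. This also stands. Labelling laterality discloses the confounding but does not remove it, so the two rows could not be read as a comparison of modes.

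**Conclusion.** The point holds as a mismatch between population and objective in descriptive analyses. Two parts differ in strength.

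The firmer part needs no mix by mode: the SAP narrows the protocol's population for the additional objectives without a reason, and by its own figure loses about 25% of subjects. The cost to the overall estimates is modest, 0.47 against 0.40 SD in half-width.

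The second part is conditional. Under the protocol 12.8 mix, with dual-threshold subjects bilateral and 20 in the CC set, it is more likely than not (61%) that no single-threshold interval can be estimated. At two or three subjects the half-width would be 9.0 or 2.5 SD. If the SAP's 28 does reflect a 35/22 blend, about 9 of 20 would be single-threshold and this part would largely disappear; the loss of a quarter of subjects would remain. The planning assumptions of the two documents should be reconciled.

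This should be corrected, but nothing here bears on the primary or secondary tests.

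**What to change.** In SAP 7.9.3, replace the sentence naming the analysis set with wording such as: *The LCC set will be used for the additional objectives, overall and by aDBS mode; results on the bilateral-only CC set will be given as a sensitivity summary.* Applying the protocol's unrestricted CC set to these objectives would serve the same purpose.

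Add three items:
- Label laterality within the single-threshold row, and state that it is expected to be about 83% unilateral, so that the single and dual rows are not to be read as a comparison of modes.
- Where a stratum is too small for an interval, list individual differences instead. The documents set no minimum size, so the sponsor should fix one before the data are seen.
- State the expected mix by mode and laterality in SAP section 6 and reconcile it with protocol 12.8.

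The cost is SAP wording and one extra set of summary tables. LCC is already defined, and the assessments are scheduled for all subjects regardless of laterality. The change can be made however the population for the primary TEED analysis is settled.
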